3.2 Study Design Rationale

The study is designed as a non-comparative, multi-center study with each site initially having a cohort of approximately 30 Subjects to recruit (maximum of 50 per site). The follow-up period of 5 years was selected to assess the early period (the first year) when any initial problems may become evident with initial fixation and stability associated with cementless fixation, as well as the medium-term period (out to five years) which is a good indicator of longer-term survivorship. Longer-term survivorship will become available as the product is captured in National Joint Registries in various markets in the absence of any other studies being planned at this point in time.

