5.2 Exclusion Criteria

Subjects will be excluded from participation in the study if they meet any of the following criteria:

- a) The Subject is a woman who is pregnant or lactating.
- b) Contralateral knee has already been enrolled in this study³.
- c) Revision knee that was previously enrolled in the study as a primary knee (ipsilateral).
- d) Subject has participated in a clinical study with an investigational product (drug or device) in the last two (2) years.
- e) Subject has had surgery on their contralateral knee within six (6) months of study enrolment or has surgery planned on their contralateral knee less than six (6) months of the study surgery.
- f) Subject is suffering from inflammatory arthritis in any joint (e.g., rheumatoid arthritis, juvenile rheumatoid arthritis, psoriatic arthritis, systemic lupus erythematosus, etc.).
- g) Active local or systemic infection.
- h) Loss of bone or musculature, inadequate bone quality (e.g. severe osteoporosis), neuromuscular compromise or vascular deficiency at the bone site in the affected limb in sufficient degree to render the procedure unjustifiable (e.g. absence of musculoligamentous supporting structures that could lead to implant instability, joint neuropathy).
- i) Severe instability secondary to advanced loss of osteochondral structure or the absence of collateral ligament integrity.
- j) The inability to make bone cuts (e.g. inadequate bone stock) so as to assure correct component position, a firm press fit, and intimate apposition of the cut bone and prosthetic surfaces.
- k) Subject is currently involved in any personal injury litigation, medical-legal or worker's compensation claims.
- Subject, in the opinion of the Investigator, is a drug or alcohol abuser (in the last five 5 years) or has a
 psychological disorder that could affect their ability to complete patient reported questionnaires or
 be compliant with follow-up requirements.

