8.4.1 Enrolment Replacement Rules

Since Subjects are enrolled at the time of consent, any Subject that is withdrawn pre-operatively and or does not receive the study required tibial / femoral implants will be replaced with a subsequent Subject. Overall, the number of Subjects who receive a TKA procedure with the study required tibial / femoral components across all sites must meet the minimum sample size of 300 patients per configuration (CR Femoral with CR or MS Tibial Insert or PS Femoral with PS Tibial Insert) and up to 300 cementless patellae (across both configurations). Intra-operative withdrawals will also be replaced with a subsequent Subject and will be assessed to understand reasons why the implant was not appropriate for use in that subset of Subjects.

Table 8-8: Data Collection for Enrolled Subjects Who are Subsequently Found to be Pre-operative and Intra-operative Screen Failures

Screen Failure Type	Screening/ Enrolment Log?	Data submitted on eCRF?	Enrolled Subject?	Example	Action
Pre-operative screen failure (discovered post-consent but pre-op)	Yes	Yes	Yes	Subject withdrew consent or the Subject no longer met inclusion/ exclusion criteria.	 Complete Subject Completion/Discontinuation eCRF Recruit an additional subject
Pre-operative screen failure (Discovered post-op)	Yes	Yes	Yes	Age criteria not met	Keep as Subject – continue to follow as per Safety population Complete Protocol Deviation eCRF
Intra-operative screen failure	Yes	Yes	Yes	Did not implant ATTUNE Cementless Tibial / Femoral device	Complete Subject Completion/Discontinuation eCRF Recruit an additional subject

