9.6 Analysis Sets

The following analysis sets are defined for the purpose of analysis: an Intent to Treat (ITT) analysis set, a Safety analysis set, and a Per Protocol (PP) analysis set. The analyses of adverse events and the Kaplan-Meier analysis of revisions will be carried out on the Safety analysis set. The primary endpoint analysis and all secondary endpoint analyses will be carried out on the Per Protocol analysis set. The analysis of the tertiary endpoints will be carried out on the PP analysis set unless otherwise stated in the final clinical summary report.

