9.6.3 PP Analysis Set

The Per Protocol (PP) analysis set is a subset of the Safety analysis set that includes all subjects who meet the following criteria:

- There are no clinically meaningful deviations from the protocol eligibility criteria, and
- The subject receives an ATTUNE Cementless FB tibial base,
- The subject has at least one post-operative evaluation in the 6 week or later time window.

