9.8.4.2 Secondary Endpoints and Associated Hypotheses

The secondary endpoints in this study are:

- Type and frequency of Adverse Events and Device Deficiencies.
 - Functional responder rates with an objective performance criteria (OPC) of 85% as measured by the KOOS questionnaire for all subjects (CR FB and PS FB combined) at the 1 year timepoint.
- The change from preoperative baseline to the 6 week, 6 month, 1 year, 2 year and 5 year timepoints in functional outcomes and quality of life assessments, as measured using additional patient reported outcomes measures (PROMS):
 - o AKS 2011
 - KOOS (all subscores)
 - FJS-12 (changes post-operatively only)
 - o *EQ-5D-5L*
- Implant survivorship of the ATTUNE Cementless FB Tibial Base using Kaplan-Meier survival analysis at 1, 2 and 5 year timepoints.
- Investigator-conducted radiographic analysis of the tibial and patellar components at 6 weeks/6 months, 1, 2 and 5 years after surgery.

All secondary endpoint analyses may be conducted after all patients have passed the recommended study window (ex. with a 2-year follow-up analysis conducted after all subjects have passed 790 days post-op). All analyses at these time points will be conducted again with final data, along with endpoints which have a 5-year follow-up time point, with locked data at the close of the study.

A Kaplan-Meier survivorship model will be used to estimate survivorship rates (where a revision is defined in Section 8.6) along with a two-sided, log-log based 95% confidence intervals; this analysis will be conducted on the Safety analysis set.

The types and frequencies of adverse events that occur throughout the study will be tabulated by MedDRA system organ class (SOC) and preferred term (PT) for all Subjects in the Safety analysis set. The proportion of Subjects experiencing each complication (PT within SOC) will be presented, and a 95% confidence interval will be estimated with the binomial exact method.

All other specified secondary endpoints will be presented with statistical summaries at each respective time point; these secondary endpoint analyses will be carried out with all data on subjects in the Per Protocol analysis set.

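### The radiographic endpoint is planned only on the Per Protocol set, so unrevised film findings in implanted knees later judged ineligible may be left out; the effect is unknown and probably small

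*Combined protocol and SAP*

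**What the plan says.** Section 9.6 reserves the Safety set for adverse events and the Kaplan-Meier analysis of revisions, and otherwise states: "The primary endpoint analysis and all secondary endpoint analyses will be carried out on the Per Protocol analysis set". Section 9.8.4.2 lists among the secondary endpoints "Investigator-conducted radiographic analysis of the tibial and patellar components at 6 weeks/6 months, 1, 2 and 5 years after surgery" and repeats the allocation for everything other than adverse events and survivorship: "these secondary endpoint analyses will be carried out with all data on subjects in the Per Protocol analysis set". No Safety-set version of the radiographic summary is planned, and radiographic failure is not defined.

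The Safety set (9.6.2) is everyone who has surgery to implant the tibial base. The Per Protocol set (9.6.3) is the part of it that received the tibial base and meets two further conditions: "There are no clinically meaningful deviations from the protocol eligibility criteria" and "The subject has at least one post-operative evaluation in the 6 week or later time window".

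The eligibility criteria in 5.2 include inadequate bone quality (h), severe instability (i) and, under (j), "The inability to make bone cuts (e.g. inadequate bone stock) so as to assure correct component position, a firm press fit". For ineligibility discovered after the operation, Table 8-8 in 8.4.1 keeps the subject, with the instruction "continue to follow as per Safety population".

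**The concern.** An implanted knee that turns out to have breached criterion h, i or j remains in the study and has its films taken and read under 8.2.5. If the breach is judged clinically meaningful, those readings leave the radiographic endpoint. The criteria that trigger removal concern the quality of the fixation bed, and the endpoint measures fixation. Section 3.4 itself ties poor bone quality to unsuitability for a cementless procedure, so the dropped knees could plausibly do worse on the outcome being summarised.

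Section 3.2 explains the early part of follow-up as the time when "any initial problems may become evident with initial fixation and stability associated with cementless fixation". Films can show such problems before a revision does. A summary that can lose the higher-risk knees is a less complete account of fixation than the data would support. Section 9.6.3 also does not say who judges a deviation clinically meaningful, or whether that happens before the films are read.

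**Working it through.** **Which Per Protocol condition matters.** A knee with no post-operative evaluation has no post-operative film, so the follow-up condition removes nothing from a film summary. Receipt of the tibial base is essentially shared with the Safety set. The eligibility condition is therefore the only one that can make the two radiographic summaries differ.

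**Which knees are affected.**
- Study tibial or femoral device not implanted: an intra-operative screen failure under Table 8-8, discontinued and replaced. On the natural reading of 9.6.2 it is in neither set, so the choice of set does not matter.
- Implanted, ineligibility found later, not judged clinically meaningful: in both sets.
- Implanted, ineligibility found later, judged clinically meaningful: in the Safety set only. This is the affected group.

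**What is lost from that group.** Revisions (any component, per 8.6) enter the Safety-set Kaplan-Meier analysis. Serious events and device- or procedure-related events are tabulated on the Safety set. Exhibit B's terms include osteolysis and polyethylene wear seen on films. What remains uncounted is a radiographic finding that is neither revised nor reported as an adverse event. Exhibit B does not name radiolucency or component migration. It covers selected terms only, so this does not make them unreportable, but their capture there is not assured.

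**Size.** The plan gives no figure for this endpoint to reproduce. Its sample-size figures (191 raised to 225) concern the primary endpoint only. The failure rate in retained knees (f), the share of implanted knees dropped (e) and the failure rate in dropped knees (r) are all assumptions.

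Safety rate = (1 − e) × f + e × r. Shift = Safety rate − f. Share of all failures omitted = e × r / Safety rate.

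With f = 3%:

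| e | r | Safety rate | Shift (points) | Share of failures omitted |
|---|---|---|---|---|
| 1% | 20% | 2.97 + 0.20 = 3.17% | 0.17 | 0.20/3.17 = 6% |
| 3% | 20% | 2.91 + 0.60 = 3.51% | 0.51 | 0.60/3.51 = 17% |
| 5% | 20% | 2.85 + 1.00 = 3.85% | 0.85 | 1.00/3.85 = 26% |
| 1% | 10% | 2.97 + 0.10 = 3.07% | 0.07 | 0.10/3.07 = 3% |
| 3% | 10% | 2.91 + 0.30 = 3.21% | 0.21 | 0.30/3.21 = 9% |
| 5% | 10% | 2.85 + 0.50 = 3.35% | 0.35 | 0.50/3.35 = 15% |

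Of 600 knees, dropping 1, 3 or 5% means 6, 18 or 30 knees. At r = 20% those contain 1.2, 3.6 or 6 expected failures.

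**Wider range.** Write r = RR × f, so that the shift is e × f × (RR − 1), and take f = 1 to 5%, e = 0.5 to 5%, RR = 1 to 10.
- RR = 1: shift 0.
- f = 2%, e = 2%, RR = 5: 0.02 × 0.02 × 4 = 0.16 points.
- f = 2%, e = 2%, RR = 10: 0.02 × 0.02 × 9 = 0.36 points.
- Extreme corner, f = 5%, e = 5%, RR = 10: 0.05 × 0.05 × 9 = 2.25 points.

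These readings treat every radiographic failure in a dropped knee as lost. Revision and adverse-event reporting would recover some of them elsewhere in the report.

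**The case against.** The best defence is that the affected group may be empty. Criteria h and j are largely surgeon judgements made before or during the operation. A surgeon who recognises the problem in time may not implant the device, and that knee is then in neither set. The only example Table 8-8 gives of ineligibility found after surgery is an age breach, which has no obvious bearing on fixation. This stands as a limit on likely size. It does not close the gap, because the table gives an example and not a restriction, and nothing in 9.6.3 exempts bone or press-fit deviations.

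The second defence is that the important failures are counted anyway: revisions and reportable adverse events are on the Safety set, and 9.8.2 requires a flow diagram giving reasons for exclusion. This largely stands. What is missing is the film results of the excluded knees, not the fact of their exclusion.

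Third, the endpoint is descriptive, with no hypothesis, threshold or success rule. That stands too, and no study conclusion turns on it.

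A reader might go further and infer that every knee found ineligible after surgery is removed and that radiographic failure is therefore understated. The documents do not support this. Only deviations judged clinically meaningful are removed, and the documents give neither a count of such knees nor a failure rate in them.

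A reader might also infer that moving to the Safety set would put films and revisions on one denominator. It would not. Films are optional at visits held outside the clinic (Table 1-1, 8.2.4.1), and subjects with a tibial base or femoral revision are withdrawn (8.6).

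**Conclusion.** The concern holds in a limited form. The radiographic endpoint is planned on the Per Protocol set alone, and that set can drop implanted knees for reasons related to fixation although they remain in follow-up. Radiographic failure may be understated. The amount is unknown and probably small: about 0.1 to 0.9 percentage points with 3% failure in retained knees, 1 to 5% of knees dropped and 10 to 20% failure among them, and zero if dropped knees carry equal risk. All three inputs are assumptions. Because events would be few, a small absolute shift could still be a noticeable share of the failures. The point does not touch the primary conclusion. Severity: minor, a cheap improvement.

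A separate matter arises under either set. Tibial base or femoral revision leads to withdrawal (8.6), and 8.5 admits no data after withdrawal, so each later film summary describes only knees not yet revised in that way. The Per Protocol choice does not cause this.

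**What to change.** 1. In 9.6 and 9.8.4.2, name the Safety set (all implanted knees with films) as the analysis set for the radiographic endpoint, with Per Protocol as supportive.
2. In that report, identify separately the knees excluded from Per Protocol, with reasons, and any knees in which a cementless component was cemented. Table 8.2 (in 8.2.3) and section 10.1 keep cemented knees in the Safety population, apart from the antibiotic-cement case that Table 8.2 discontinues, and 9.6.3 does not mention cementing. Readers need to see them apart from truly cementless knees.
3. State who judges an eligibility deviation clinically meaningful, and that the judgement is made before the films are read.
4. Separately, beside each visit's result, give the number of knees already revised for loosening or migration.

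The cost is a few sentences in 9.6, 9.6.3 and 9.8.4.2 and some extra table rows. No new data are needed, because the films and readings are already part of follow-up. The downside is a figure that may be slightly less favourable and is slightly more heterogeneous.

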9.8.4.3 Additional Endpoints

Additional endpoints include:

- Implant survivorship of the ATTUNE Cementless FB Tibial Base using Kaplan-Meier survival analysis at 3 and 4 year timepoints.
- To evaluate the duration of surgery ("skin-to-skin" time) for all surgeries, with analysis stratified by cemented/Cementless patella usage.

Duration of surgery ("skin to skin" time) may be analyzed any time after all subjects have been enrolled and undergone surgery. All other post-operative tertiary endpoints may be conducted after all subjects have passed the preferred post-op window. All analyses at these time points will be conducted again with final data, along with endpoints which have a 5-year follow-up time point, with locked data at the close of the study.

9.8.5 Plans for Interim Analysis

There are no formal interim analyses planned with the intent of early trial closure.

Interim summaries may be performed as required, for example to provide information to Regulatory Authorities or Notified Bodies.

10 DEVICE DESCRIPTION

All implant components are commercially available for use in the United States. The intended purpose, indications, contraindications and population are described in the Instructions for Use (IFU), which is contained in the packaging of all products marketed in the United States.

10.1 Fixation

ATTUNE Cementless Cruciate Retaining (CR) or Posterior Stabilized (PS) Femoral implants are to be used in combination with the ATTUNE Cementless Fixed Bearing (FB) Tibial Base implant and appropriate Tibial Insert and must be used without bone cement. If any Cementless components are cemented, a Protocol Deviation eCRF must be completed and the subject will continue to be followed as part of the Safety Population. See Table 8-2 Protocol Requirements During Surgery for additional details regarding fixation requirements.

10.2 Devices

A list of devices permitted for Subjects enrolled in the study is presented in Table 10-1. All Investigators will be trained on the use of these devices prior to their first enrolment. The components permitted for each of the two (2) constructs is defined in Table 10-1. The details of the individual components are provided in Table 10-2. Additional, detailed information regarding component product codes are provided in Exhibit B.

Table 10-1: Components of the Construct

	Components Needed for Construct				
Configuration	Femoral (Cementless)	Tibial Base (Cementless)	Insert	Cemented Patella*	
 Cruciate Retaining fixed bearing (ATTUNE® CR FB) 	CR	FB	Cruciate Retaining or Medial Stabilized	Medial Offset OR	
 Posterior Stabilized fixed bearing (ATTUNE® PS FB) 	PS	FB	Posterior Stabilized	Anatomic	

^{*} Patella resurfacing shall follow site standard of care (unresurfaced or cemented patella). For Subjects where the patella will be resurfaced, 2 patella implant designs are permitted.

Table 10-2: Knee Configurations

Regulatory Status	Device Component	Component Offerings		Details
		Cruciate Retaining (CR)	(CR) and posterion components are	omponents are available in cruciate retaining r stabilized (PS) configurations. The femoral manufactured from cast Co-Cr-Mo alloy STM standard F-75 and the bone opposing
CE mark & 510(k) clearance	Cementless Femoral Components	Posterior Stabilized (PS)	porous coating tec Fourteen sizes are narrow sizes: 3N sterilized using g cementless use or The PS femoral	ed with Co-Cr-Mo POROCOAT, a proprietary chnology. They are available in lefts and rights. It available including standard sizes 1-10 and I, 4N, 5N, 6N. Femoral components are samma irradiation. They are available for only. Components have a cam mechanism that corresponding spine on the PS tibial insert.
510(k) clearance	Cementless Tibial Base	Fixed Bearing (FB)	ATTUNE tibial com and 3D printed tita and the bone oppo porous coating ted proximal surface is ATTUNE FB tibial i	nponents are manufactured from wrought anium conforming to ASTM standard F-3001 osing surfaces are comprised of 3D printed chnology and fixation geometry features. The s designed to work with currently available nserts, CR and PS. The cementless FB tibial e in sizes 1-10. Tibial components are
			Cruciate Retaining (CR)	The CR and PS tibial inserts are symmetrical tibial inserts manufactured from AOX Antioxidant UHMWPE and are available in
CE mark & 510(k) clearance	Tibial Inserts	Fixed Bearing (FB)	Posterior Stabilized (PS)	sizes 1-10 and thicknesses from 5, 6, 7, 8, 10, 12, 14, 16, 18mm. Additional thicknesses 20 & 22mm are available for the PS inserts. The distal surface has features that secure the insert to the FB tibial base. Tibial inserts are sterilized using gamma irradiation.
510(k) clearance	Tibial Inserts	Fixed Bearing (FB)	Medial Stabilized (MS)	The ATTUNE Medial Stabilized tibial inserts are asymmetrical fixed bearing tibial inserts that will form part of the ATTUNE Knee system. They are designed to work with the ATTUNE CR femur and any of the ATTUNE Fixed Bearing Tibial Base options. They are manufactured from AOX Antioxidant

DSJ_2019_05, Rev D (FINAL) 24 August 2022 DePuy Synthes Products, Inc. - Confidential

			UHMWPE and are available in right and left sizes 1-10 and thickness from 5, 6, 7, 8, 10, 12, 14 and 16. Tibial inserts are sterilized using gamma irradiation.	
CE mark & 510(k) Cemented Patellaes	Medial Offset	The patellar components are manufactured from UHMWPE and are available in two styles, medialized dome and medialized anatomic. They are available in 5 sizes with proportionally		
	Anatomic	increasing thicknesses from 8.5 to 10.5 mm. Patellar components are sterilized using gamma irradiation. They are available for cemented use only.		
		Medial Offset	The cementless patellar components are manufactured from UHMWPE overmolded onto 3D printed titanium conforming to	
510(k) clearance	Cementless Patellaes	Anatomic (if available during enrolment)	ASTM standard F-3001 and the bone opposing surfaces are comprised of 3D printed porous coating technology. The anterior surface is designed to work with currently available ATTUNE CR and PS femoral components. They are available in 4 sizes with proportionally increasing thicknesses from 9.0 to 10.5 mm. Patellar components are sterilized using gamma irradiation.	

10.3 Use of the Study Devices

In addition to the CIP training provided, all Investigators will receive training with the Study Devices, to be arranged by the Sponsor, prior to implanting the ATTUNE FB Tibial Base as part of this clinical investigation.

10.4 Device Management

Device Deficiency reporting for this clinical study includes both the implantable components and the instrumentation. Specific device accountability is not required for this study as it is entirely post-market. Implant catalog and lot numbers will be collected.

10.4.1 Reporting on Deficient Devices

All study Sites (regardless of Site location) are required to report Device Deficiencies relating to ANY of the implantable ATTUNE components, component packaging, and instrumentation to the Sponsor via the Device Deficiency eCRF (see Section 8.3). In the event a device deficiency is associated with a Study Subject experiencing an adverse event, the Adverse Event eCRF is also required to be submitted to the Sponsor.

